### 8.3.3.3 EXPECTEDNESS

An AE that may be reasonably anticipated to occur as a result of the study procedures or study participation and should thus be described in the research proposal, the informed consent document, or is part of the normal disease process or progression. An AE or suspected adverse reaction is considered "unexpected" if it is unlikely to occur in the study population, or it is unlikely to occur at the severity that has been observed.

An adverse event is defined as being unexpected if the event exceeds the nature, severity or frequency described in the current IRB Application including the protocol and consent form. An unexpected AE also includes any AE that meets any of the following criteria:

- Results in subject withdrawal from study participation,
- Due to a deviation from the IRB approved study protocol

### 8.3.4 TIME PERIOD AND FREQUENCY FOR EVENT ASSESSMENT AND FOLLOW-UP

The occurrence of an adverse event (AE) or serious adverse event (SAE) may come to the attention of study personnel when participants complete the adverse event questionnaire or when participants spontaneously report adverse events.

All AEs, not otherwise precluded per the protocol, will be captured on an adverse event report form. Information to be collected includes event description, time of onset, clinician's assessment of severity, relationship to study procedures, and time of resolution/stabilization of the event. All AEs occurring while on study will be documented appropriately regardless of relationship. All AEs will be followed to adequate resolution.

Any medical or psychiatric condition that is present at the time that the participant is screened will be considered as baseline and not reported as an AE. However, if the study participant's condition deteriorates at any time during the study, it will be recorded as an AE.

Changes in the severity of an AE will be documented to allow an assessment of the duration of the event at each level of severity to be performed. Documentation of onset and duration of each episode will be maintained for AEs characterized as intermittent.

[name] will record events with start dates occurring any time after randomization until the last day of study participation. At endpoint, the investigator will inquire about the occurrence of AE/SAEs since randomization.

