### 2.3.3 ASSESSMENT OF POTENTIAL RISKS AND BENEFITS

**MBSR+PS** Participants will be provided with a thorough description of the intervention prior to randomization, and notified that they can withdraw participation at any time without penalty. Given the physical and psychological consequences of poor sleep quality during pregnancy, we expect that the proposed intervention would be associated with improved outcomes. However, important precautions will be taken to minimize physical risks. Participants will be provided the American College of Obstetrics and Gynecology list of indicators to terminate exercise. Participants will be advised to stop the physical activity if these signs are present, and to contact their obstetric health care provider. We will ask participants to alert us if they experience an increase in daytime sleepiness, and will advise them about the risks of driving or doing any activity where severe sleepiness puts them at danger, and will instruct them to take naps if they feel sleepy.

**Self-report questionnaires:** Participants will be allowed to skip any questions they do not feel comfortable answering. One exception is that participants will be informed during the initial screening that skipping questions that are necessary for determining eligibility may preclude their ability to participate in the study. Additionally, because all questionnaires will be completed online, participants can complete them in a location and at a pace that feels comfortable to them.

**Actigraphy (optional depending on COVID-19 guidelines; see Section 8.1):** In case of allergy, participants can wear the monitor over their sleeve or use a wrist sports sweatband to protect their skin.

**Confidentiality:** All data will be handled with the utmost attention to participants' confidentiality. Participants will be assigned unique, coded, confidential identifiers that will be used to label all data forms, data entries, and questionnaires. The key linking the participants' identity to their unique coded identifier will be stored on a cloud-based collaboration tool that uses access controls and encryption, and is safe for storing protected health information. Access to all data will be limited to the PI and trained,

authorized study staff.

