## 4.3 JUSTIFICATION FOR INTERVENTION

We will deliver MBSR+PS via video conferencing (i.e., Zoom platform) instead of via in-person sessions for several reasons. First, delivering the intervention remotely affords

us more flexibility and the ability to continue study activities even in the context of potential COVID-19 shelter-in-place orders. Second, pregnant women may have a lower tolerance for risk for attending in-person visits when there are spikes in COVID-19 activity. Third, we want to develop a program that has high potential for scalability and ultimately plan to deliver the intervention remotely in efficacy testing. Thus, the feedback we will get in this feasibility trial will be more relevant. Finally, delivering the intervention remotely is responsive to focus group feedback that women do not want an all in-person intervention.

MBSR will be offered in its typical session format: in 8 weekly sessions with an all-day retreat. The prenatal sleep content will be offered in 6-8 weekly brief sessions designed to be 30 minutes or less. Data will be analyzed on an intent-to-treat basis, and we aim for an average percentage of sessions attended  $\geq 50\%$ .

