#### 6.1.2 ADMINISTRATION AND/OR DOSING

The full-dose MBSR+PS program will consist of:

Standard MBSR:

- 8 weekly sessions
- All day retreat
- Administered by a trained and vetted MBSR instructor via Zoom
- Delivered to heterogeneous groups, including non-pregnant women

Prenatal Sleep Content:

- 6-8 weekly brief sessions ( $\leq$  30 minutes) via Zoom
- Flexibly designed to be delivered 1:1 or to small groups of pregnant women

- Delivered by an instructor with behavioral sleep medicine training

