- Disruptors of sleep (physical symptoms, anxiety/worry, mind racing)
- Psychological responses to nightly physical symptoms

Depending on local COVID-19 guidelines, we may also use wrist-actigraphy to assess our secondary clinical outcome, objective sleep behaviors (total sleep time, sleep latency, wake after sleep onset, number of awakenings, sleep efficiency). We will collect these data only if local guidelines permit research as usual. Sending and receiving the wrist actigraphs requires multiple trips per week to FedEx, and we do not want to risk staff safety to collect this secondary outcome. Further, we have adequate feasibility data collecting actigraphy data from 50 pregnant women in our preliminary research (Aim 1 of K23).

**Outcome measures:** Consistent with our preliminary research (Aim 1 of K23), we will collect data on nightly physical symptoms, psychological mediators, and sleep quality using retrospective, self-report measures. We received feedback from Aim 1 participants that completing these online measures was not burdensome, and we had no missing data.

- Pregnancy Symptoms Inventory previously adapted to measure nightly sleep disturbances
- Measures of psychological mediators:
  - Self-Compassion Scale - Short Form
  - Rumination-Reflection Questionnaire
  - Five Facet Mindfulness Questionnaire
  - Coping Strategy Scale
- Measures of sleep:
  - Pittsburgh Sleep Quality Index
  - Insomnia Severity Index
  - Dysfunctional Beliefs About Sleep
  - Measures for coping with sleep disturbances
  - Worry about sleep
- Other clinical outcomes:
  - Patient Health Questionnaire-9

- PROMIS 6-item anxiety measure
- Perceived Stress Scale
- Contemplative practices and stress management techniques

**Daily measures:** Participants randomized to MBSR+PS will be asked to complete a brief daily home practice measure and the consensus sleep diary from the first until the last intervention session.

**Weekly measures:** Participants will complete a depression measure (Patient Health Questionnaire-9) once per week from randomization until endpoint.

**Endpoint measures:** Participants will complete the same outcome measures as at the baseline timepoint, as well as the Client Satisfaction Questionnaire and adverse events questionnaire.

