#### 10.1.6 SAFETY OVERSIGHT

Safety oversight will be under the direction of an Independent Monitoring Committee (IMC) composed of individuals with the appropriate expertise, including sleep during pregnancy, biostatistics, and obstetrics and gynecology. Members of the IMC will be independent from the study conduct and free of conflict of interest. The IMC will meet at least semiannually to assess safety and efficacy data from each arm of the study. The IMC will operate under the rules of an approved charter that will be written and reviewed at the organizational meeting of the IMC. At this time, each data element that the IMC

needs to assess will be clearly defined. The IMC will provide its input to the National Institutes of Health staff.

---

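### Adverse events are sought more intensively in MBSR+PS than in TAU before endpoint and report source is not a listed field, so by-arm counts may be biased, probably toward more events on MBSR+PS

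*Combined protocol and SAP*

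**What the plan says.** Section 8.3.4 names two routes by which an AE is found: it "may come to the attention of study personnel when participants complete the adverse event questionnaire or when participants spontaneously report adverse events". Both lead to one AE report form. "Information to be collected includes event description, time of onset, clinician's assessment of severity, relationship to study procedures", and the list ends with resolution; the source of the report is not on it.

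The questionnaire route is common to both arms and comes once. Section 8.1 gives the endpoint measures "as well as the Client Satisfaction Questionnaire and adverse events questionnaire", and 8.3.4 adds: "At endpoint, the investigator will inquire about the occurrence of AE/SAEs since randomization".

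The contact schedule differs by arm. Section 4.3 states: "MBSR will be offered in its typical session format: in 8 weekly sessions with an all-day retreat". Section 6.1.2 adds "6-8 weekly brief sessions" of prenatal sleep content. MBSR+PS women also complete daily home-practice and sleep-diary surveys (8.1), and under the MBSR+PS heading of 2.3.3 the plan says: "We will ask participants to alert us if they experience an increase in daytime sleepiness". For TAU, apart from notification of assignment, which both arms receive, no live contact is scheduled between randomization and endpoint. Both arms complete the weekly online PHQ-9.

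Section 9.4.4 (safety analyses) is marked not applicable. The by-arm look at safety is in 10.1.6: the IMC meets at least twice a year to "assess safety and efficacy data from each arm of the study".

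**The concern.** Spontaneous reporting depends on opportunity. A woman who meets a study instructor every week has regular occasions to mention an event; a woman in TAU must make contact herself or wait for the endpoint questionnaire. Section 6.3 also has unblinded study staff helping the clinician deliver the intervention, so study personnel are at hand in one arm. The sleepiness prompt adds an active request for one type of event in that arm.

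The common questionnaire evens this out only for women who reach endpoint and recall the event. It does nothing for women who miss endpoint, or for women still in follow-up when the IMC meets.

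At stake is the reading of the by-arm counts. An excess on MBSR+PS could be taken as harm when it is partly better detection, or a real excess could be dismissed as over-reporting. Without a source field, neither reading is easy to check.

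**Working it through.** **Contacts after randomization.** MBSR: 8 sessions + 1 retreat = 9. Sleep supplement: 6 to 8. Total in MBSR+PS: 15 to 17, of which only the 6 to 8 sleep sessions are study-run; the other 9 are public classes and a retreat (4.1). TAU: 0.

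**The plan's own figure.** Sections 5.5 and 9.2: 50 × 0.80 = 40 with endpoint data, which reproduces. It leaves 50 − 40 = 10 women for whom the endpoint questionnaire is not expected.

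**Detection model.** The documents give no AE rate, recall or capture rate, so these are assumptions. Let r be endpoint retention, q the probability that the questionnaire elicits an event that occurred, and s the probability that it is reported spontaneously. Then

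P(recorded) = 1 − (1 − s)(1 − r·q).

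True risk and q are the same in both arms, r = 0.80 in both, s = 0.1 in TAU, and s = 0.3 or 0.6 in MBSR+PS.

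| q | TAU (s = 0.1) | MBSR+PS (s = 0.3) | Ratio | MBSR+PS (s = 0.6) | Ratio |
|---|---|---|---|---|---|
| 1.0 | 1 − 0.9 × 0.20 = 0.820 | 1 − 0.7 × 0.20 = 0.860 | 1.05 | 1 − 0.4 × 0.20 = 0.920 | 1.12 |
| 0.8 | 1 − 0.9 × 0.36 = 0.676 | 1 − 0.7 × 0.36 = 0.748 | 1.11 | 1 − 0.4 × 0.36 = 0.856 | 1.27 |
| 0.5 | 1 − 0.9 × 0.60 = 0.460 | 1 − 0.7 × 0.60 = 0.580 | 1.26 | 1 − 0.4 × 0.60 = 0.760 | 1.65 |

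**Where the ratio is 1.00.** If s and r are equal in the two arms the two expressions are identical. If r·q = 1 in both, every event is recorded whatever s is.

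**Unequal retention (assumed 70% in MBSR+PS, 90% in TAU).** With unequal capture the ratio runs from 0.87 (q = 1.0, s = 0.3 against 0.1: 0.790/0.910) to 1.47 (q = 0.5, s = 0.6 against 0.1: 0.740/0.505). With equal capture of 0.1 and q = 1.0 it is 0.730/0.910 = 0.80. The direction can therefore reverse.

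**Before endpoint.** For a woman still in follow-up r·q = 0, so the ratio reduces to s in MBSR+PS divided by s in TAU. No common route dilutes the difference, and no document gives either value.

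**What would be seen in a trial of this size.** The allocation ratio is not stated; 25 per arm is assumed. At a true risk of 20%, the most unequal row above gives expected counts of 25 × 0.20 × 0.760 = 3.8 against 25 × 0.20 × 0.460 = 2.3 participants. From exact binomial distributions with 80% retention in both arms, the chance that MBSR+PS shows strictly more participants with an event is 45% to 67% at a true risk of 20% and 49% to 80% at 40%. With equal capture it is about 40% to 44%.

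**Questionnaire events only.** The ratio becomes (r·q in MBSR+PS)/(r·q in TAU), which is the ratio of retentions: 0.80/0.80 = 1.00, or 0.70/0.90 = 0.78. Restricting the comparison in this way removes the contact effect but not a retention difference.

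**The case against.** A reader might infer that the by-arm safety comparison must show more events on MBSR+PS by construction. The documents do not support that. The endpoint enquiry reaches back to randomization in both arms. Both arms also have the weekly PHQ-9, with a staff call if the self-harm item is endorsed, and the instruction in 8.2 to contact staff about worsening symptoms. Spontaneous capture in TAU is therefore not zero, and assuming zero inflates the result: with complete retention, q = 0.5 and s = 0.5, the ratio is 0.75/0.50 = 1.50 against s = 0 in TAU, but 0.75/0.65 = 1.15 against s = 0.3.

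Several further objections stand in part:

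- No comparative safety analysis is planned, and the IMC charter, which will define its data elements, is not in these documents. The affected use is the IMC's by-arm review and any later by-arm report.
- Nothing makes the instructors of the public MBSR classes relay events, so 15 to 17 contacts against 0 overstates the difference. The study-run sleep sessions still leave 6 to 8 against 0.
- It would be too strong to say the two streams can never be separated. Section 10.1.9.1 has all data collected in Qualtrics or REDCap, so questionnaire responses should exist as their own records, and the field list in 8.3.4 may not be exhaustive. Matching afterwards is possible, but less reliable than a recorded field.
- Sections 8.3.2 and 8.3.5 treat increased sleepiness as an expected effect of sleep consolidation, so an excess of it could be partly real.
- Section 8.3.1 defines AEs as effects of the research, while 8.3.4 documents them whatever their relationship to it. The narrower definition could by itself lower TAU counts. The two passages must be reconciled.

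The objections limit the claim, but do not remove the unequal ascertainment before endpoint or supply a way to see it in the data.

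**Conclusion.** The point holds as a likely bias of unknown size. Before endpoint, AE ascertainment is more intensive in MBSR+PS, and the plan neither lists report source as a field nor separates the routes in reporting. By-arm AE counts are probably tilted toward MBSR+PS. The range of about 1.05 to 1.65 rests on assumed recall of 0.5 to 1.0, assumed spontaneous capture of 0.3 or 0.6 against 0.1, and the planned 80% retention applied equally to both arms. Absolute differences in a 50-woman pilot would be small, and an observed excess is made more likely rather than certain. No planned test is affected and the primary endpoints are untouched. The matter is still worth correcting because the by-arm IMC review is the only one specified, and source is easiest to capture when the event is reported.

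**What to change.** In 8.3.4, add to the AE report form the source of first report (endpoint questionnaire, spontaneous, or session contact) and a flag for whether the event was also reported on the endpoint questionnaire. The flag settles how an event reported by both routes is classed.

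In 9.4.4, now marked not applicable, and in the IMC tables:

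- show AEs by arm, split by source;
- base the between-arm comparison on all events reported on the common endpoint questionnaire, including those also reported earlier;
- give questionnaire completion by arm beside it;
- list all other events by arm, labelled as unequally ascertained.

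All events are still recorded and reported as now. The cost is one field, one flag and one extra table. The downside is that the comparative table omits women without endpoint data (about 20% expected) and events reported only spontaneously, and harms may concentrate among those women. The all-source listing must therefore stay beside it.

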## 1.2 SCHEMA

### ***Flow Diagram***

### 1.3 SCHEDULE OF ACTIVITIES

Timepoint	Screening	Baseline	Daily	Weekly	Endpoint
Allowable window	N/A	0-4 weeks prior to randomization	Within 24 hours	Within 3 days	+/- 4 weeks
Screening consent	x				
Screening measures	x				
Demographic form	x				
Orientation session	x				
Study consent	x				
14-day daily diary		x			x
Outcome measures		x			x
Depression measure				x	
Home practice measure (MBSR+PS only)			x		
Sleep diary (MBSR+PS only)			x		
Use of non-study treatments questionnaire		x			x
Adverse events questionnaire					x
Client Satisfaction Questionnaire					x

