## 7 STUDY INTERVENTION/EXPERIMENTAL MANIPULATION DISCONTINUATION AND PARTICIPANT DISCONTINUATION/WITHDRAWAL

### 7.1 DISCONTINUATION OF STUDY INTERVENTION/EXPERIMENTAL MANIPULATION

We do not anticipate any reasons for the investigators to discontinue the study intervention for participants. Participants can decide to discontinue the study intervention and to continue participating in the study by completing follow-up

measures. Participants who become ineligible (e.g., no longer pregnant due to miscarriage) will have the option to continue both the intervention and the study.

If a participant discontinues the intervention, we will record their reason(s) for discontinuing the intervention.

If the participant is due to complete assessments within 2 weeks of discontinuing the study intervention, those assessments will be administered at the time of discontinuation; if the next scheduled assessments are more than 2 weeks from the discontinuation date, the discontinued participant will wait for the next scheduled assessment. Thereafter, the participant will be included in all future scheduled assessments, even though not participating in the intervention.

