## 8 STUDY ASSESSMENTS AND PROCEDURES

### 8.1 ENDPOINT AND OTHER NON-SAFETY ASSESSMENTS

See the Table in Section 1.3 for an overview of timepoints, allowable response windows, and measurement schedule.

**Screening timepoint:** Participant demographic data will be collected to determine eligibility (e.g., age) and to fully characterize the sample (e.g., race, ethnicity, highest

level of education attained, income, marital status, number of children and their ages, zip code, insurance type, employment status). Eligibility criteria will be assessed using a screening survey that assesses:

- self-report of pregnancy status and gestational age in weeks
- confirmation of pregnancy via an ultrasound image, after visit summary, appointment reminder, bill, or similar document that includes participant name and date. Women can choose to upload this documentation into the eligibility survey, display the documentation during the orientation visit, or send the document via secure email.
- self-reported daily access to a web-enabled computer, phone, or tablet self-reported ability to read and speak English
- self-reported diagnosis of sleep apnea, narcolepsy, parasomnia, or circadian rhythm disorder
- validated Facco algorithm to screen for sleep apnea during pregnancy
- validated Morning-Eveningness Questionnaire to screen for circadian rhythm disorder
- self-reported experience of sleepwalking, sleeptalking, nightmares to assess for parasomnia
- self-reported night shift work in the past month or next month
- self-reported nighttime caregiving responsibilities
- validated Patient Health Questionnaire-9 to assess for depression and/or suicidality
- self-reported diagnosis of schizophrenia or bipolar disorder
- self-reported on bed rest
- self-reported pregnancy with multiples

**Baseline timepoint:** Participants will complete two types of assessments at the baseline timepoint: 14 daily sleep diaries and outcome measures.

**14 day online daily sleep diaries:** To assess the mechanisms of pregnancy-related physical symptoms-poor sleep association, we will use daily diary methods to capture data on the dynamic, longitudinal associations between nightly physical symptoms, psychological responses (i.e., acceptance, self-compassion, rumination, worry, mindfulness, maladaptive pain coping), and sleep quality. Each morning for 14 consecutive days, participants will complete a diary assessing:

- Last night's sleep using the validated consensus sleep diary

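### Between randomization and endpoint, no scheduled question described in the protocol asks about pregnancy status, bed rest or hospitalization; such events surface only unprompted or incidentally, with more occasions in MBSR+PS than in TAU

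*Combined protocol and SAP*

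**What the plan says.** Section 8.3.4 names two ways in which an adverse event reaches the study: "when participants complete the adverse event questionnaire or when participants spontaneously report adverse events". It then times the active inquiry: "At endpoint, the investigator will inquire about the occurrence of AE/SAEs since randomization". In the Schedule of Activities (1.3) the row "Adverse events questionnaire" has one mark, in the endpoint column, and section 8.1 lists the questionnaire with the endpoint measures.

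Two relevant questions are asked earlier, at screening (8.1): "self-report of pregnancy status and gestational age in weeks" and "self-reported on bed rest". Neither is scheduled again. The only hospitalization item named is psychiatric, within the non-study treatments questionnaire (6.5 places it at endpoint; 1.3 marks baseline and endpoint).

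Between randomization and endpoint, one scheduled measure goes to both arms: "Participants will complete a depression measure (Patient Health Questionnaire-9) once per week from randomization until endpoint". For a woman who stops the intervention, section 7.1 says "we will record their reason(s) for discontinuing the intervention"; if assessments are due within 2 weeks, "those assessments will be administered at the time of discontinuation". Section 7.1 also foresees miscarriage and lets such women stay in the intervention and the study.

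**The concern.** The protocol treats these events as important. It excludes women on bed rest (5.2), foresees miscarriage (7.1) and makes hospitalization a criterion of seriousness (8.3.2). Section 8.3.4 undertakes to document onset, changes in severity and duration, regardless of relationship to the study. A single look back after about 8 weeks is a weak instrument for that.

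Two things are at stake. The first is awareness. The clinicians who are unblinded for safety (6.3) would usually learn of an event sooner if it were asked about. For serious, unexpected events related to the intervention, the reporting time runs from awareness (8.3.6), so late awareness means a late report. The second is comparability. The Independent Monitoring Committee (IMC) looks at safety data from each arm at least twice a year (10.1.6). Before endpoint, an MBSR+PS woman has more occasions than a TAU woman to mention an event, so interim counts can differ between arms for that reason alone. The feasibility endpoints are not affected.

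**Working it through.** **The plan's own figure.** Section 9.2: 50 × 0.80 = 40 women with endpoint data. This reproduces. It leaves 50 − 40 = 10 women at most, at the planned retention, who would be sent the endpoint questionnaire but not answer it.

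**Routes before endpoint.**

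| Route | MBSR+PS | TAU | Does it ask about these events? |
|---|---|---|---|
| Spontaneous report (8.3.4); contact about worsening symptoms (8.2) | yes | yes | No; the woman must volunteer it |
| Weekly PHQ-9 and its follow-up (8.1, 8.2) | yes | yes | No; depression and suicidality |
| Outreach after a missed survey (7.3) | yes | yes | No; a reminder to complete measures |
| Reasons for attrition (Section 3) | yes | yes | Qualitative; no timing given |
| Recorded reason for stopping the intervention (7.1) | yes | nothing to stop | Only if it is the reason given |
| 6 to 8 sleep sessions (6.1.2); weekly attendance entry (6.4) | yes | no | No such question described |
| Daily home practice measure and sleep diary (8.1) | yes | no | No such question described |

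The item content of the questionnaires is not given, so the statement is that no such question is described. One exception in timing: an MBSR+PS woman who stops within 2 weeks of endpoint gets the endpoint assessments early (7.1).

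**Wait for an active question under the plan.** Inputs: endpoint at 8 weeks after randomization (9.2), with a window of ±4 weeks (1.3). Assumed: onset uniform over weeks 0 to 8, mean week 4, and the course starting at randomization.

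- Endpoint at week 8: 8 − 4 = 4 weeks = 28 days.
- Late edge, week 12: 12 − 4 = 8 weeks.
- Course starting L = 0 to 4 weeks after randomization (assumed), endpoint at 8 + L, onset uniform over that whole period: (8 + L)/2 = 4 to 6 weeks.

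At the early edge, week 4, half of the assumed onsets (4/8) fall after the question. This is secondary, because participation ends once endpoint measures are complete (4.4) and 8.3.4 records events only up to the last day of participation.

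**Wait with a weekly item.** The response window is 3 days (1.3). If every survey is answered: 7/2 = 3.5 days, plus 0 to 3, gives 3.5 to 6.5 days. With a proportion r answered each week (assumed, weeks independent), the mean is 7 × (0.5 + 1/r − 1):

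- r = 0.95: 3.9 days, plus 0 to 3 = 3.9 to 6.9
- r = 0.80: 5.3 days, plus 0 to 3 = 5.3 to 8.3
- r = 0.60: 8.2 days, plus 0 to 3 = 8.2 to 11.2

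**Difference from the 28-day case.** From 28 − 11.2 = 16.8 to 28 − 3.5 = 24.5 days, or about 17 to 24 days.

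**The case against.** For a 50-woman, low-risk behavioral pilot, an endpoint inquiry plus spontaneous report is a defensible choice. The protocol knows of no evidence of fetal or obstetric risk (2.3.1), women are told to contact their obstetric provider if warning signs appear (2.3.3), and no safety analysis is planned (9.4.4). A woman in hospital or on bed rest is ordinarily already under medical care.

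Several points stand and limit the concern:

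- Spontaneous report is a direct, named route for both arms, and reasons for attrition are not confined to MBSR+PS.
- At endpoint both arms get the same question, back to randomization. Pregnancy loss, bed rest and hospitalization are memorable, so for women who answer, most of the imbalance disappears.
- The expedited reports in 8.3.6 concern events related to the intervention. These arise almost entirely in MBSR+PS, where contact is heaviest.
- Section 8.3.1 defines adverse events as effects of the research, so many of these events may not qualify, although 8.3.4 documents events regardless of relationship.
- Routine reporting of unrelated events to the IMC and the funder is annual (8.3.6), so a few weeks matter there only near a cut-off.

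A reader might infer that the study has no means of learning of these events before endpoint, or that final counts by arm will be biased. The documents support neither: the routes in the table exist, and the common endpoint question corrects most of the difference among responders. A reader might also take 17 to 24 days as the delay in detection. It is the difference in waiting time for an active question, and equals earlier detection only if none of the existing routes works.

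**Conclusion.** The gap is real and modest. No scheduled question on these events is described between randomization and endpoint, and the other routes are more numerous in MBSR+PS. Three consequences survive: later awareness, interim counts by arm that depend partly on how much contact each arm has, and events that may never be recorded among endpoint non-responders.

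The non-responder figure of up to 10 of 50 rests on the plan's 80% retention. The waiting times rest on assumed uniform onset, endpoint timing and weekly response. The documents give no incidence, so no number of affected women, missed reports or changed decisions can be claimed. The 7.1 policy of letting women continue works without scheduled detection and is not in question. The change below is an inexpensive improvement to consider; the trial's conclusions on feasibility, acceptability and adherence do not depend on it.

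**What to change.** Add two yes/no items to the weekly PHQ-9 survey in both arms:

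1. Still pregnant? If not, a sensitively worded follow-up separates loss from birth. Drop the item once either is reported.
2. Put on bed rest or hospitalized, for a physical or mental health reason, since the last survey?

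A report of loss, bed rest or hospitalization alerts the unblinded clinicians in 6.3, who contact the woman, offer the 7.1 option, and log and classify any adverse event. Births need separating because a woman randomized at 28 weeks is at 28 + 8 = 36 weeks at a week-8 endpoint and 28 + 12 = 40 at the late edge. Keep the endpoint questionnaire and the 7.1 policy, and report adverse events by arm and by source (weekly item, volunteered or incidental, endpoint).

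The cost is an IRB amendment, a small survey change and some follow-up time from existing clinicians. At most 50 × 8 × 2 = 800 extra answers are needed, or 50 × 12 × 2 = 1,200 if surveys run to week 12. Limiting alerts to defined events keeps ordinary pregnancy symptoms from triggering them. More adverse events will be recorded than now, weekly non-response remains, and women who have already finished gain nothing.
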